#### **Aim 1:**

##### **MICROBIOTA ANALYSIS OF VAGINAL AND URINARY SPECIMENS:**

The vaginal and urinary microbiota will be characterized through molecular techniques (e.g., sequencing amplicons of the V3-V4 region of the bacterial 16S rRNA gene, shot gun or whole genome metagenomics, RNA-seq, functional analyses including metabolomics and proteomic analyses).

**Vaginal D- and L-lactic acid assays:** Measuring vaginal L- and D-isomers separately allows us to assess the association between VET and the concentration of these individual isomers. **Vaginal “estrogenization”:** This will be assessed with the Vaginal Maturation Index, a standard cytologic measure of epithelial cellular maturation.

**Aim 2:**

**SOLUBLE MEDIATORS OF IMMUNITY**

Concentrations of soluble biomarkers will be determined. We currently plan to use the fluorescent bead based Luminex multiplex system, but specific methods may be modified according to laboratory standards.

**5. Inclusion/Exclusion Criteria**

**Eligibility:** Participants in this study will be postmenopausal women (menopausal for at least 1 year) with a minimum age of 55 years. Participants will have documentation of recurrent UTI, defined as follows

- History of treatment for at least 3 UTIs in the past year or 2 episodes within 6 months AND
- At least one positive urine culture during an acute symptomatic episode.

**Exclusion criteria:**

- Women receiving antibiotic prophylaxis to prevent UTI recurrence;
- Women with contraindications to vaginal estrogen (as indicated on the FDA-mandated package insert) and those who have used vaginal or systemic estrogen within the past 6 months;
- Women with an active UTI and those who have received antibiotics within the prior 2 weeks;
- Women with complicated rUTI, defined by immune compromise, anatomic or functional abnormalities of the urinary tract, indwelling catheterization, those performing self-catheterization, and those with neurological disease or illness relevant to the lower urinary tract;
- Women with only asymptomatic bacteriuria (rather than recurrent symptomatic UTI)
- Women who have had UTI diagnosed only in the setting of institutionalization, including hospitalization
- Women with a blood clotting disorder (e.g., Factor V Leiden, prothrombotic mutation, protein C, protein S or antithrombin deficiency)

**6. Drugs/ Substances/ Devices**

- a. The rationale for choosing the drug and dose or for choosing the device to be used.
- b. Justification and safety information if FDA approved drugs will be administered for non-FDA approved indications or if doses or routes of administration or participant populations are changed.
- c. Justification and safety information if non-FDA approved drugs without an IND will be administered.

The vaginal estrogen therapy to be used in this study is vaginal estradiol tablets (10mcg), administered daily for two weeks, followed by twice weekly. This product is FDA approved and marketed for treatment of menopausal vaginal atrophy and are commonly used in post-menopausal women for a variety of related indications.

## 7. Study Statistics

- Primary outcome variable.
- Secondary outcome variables.
- Statistical plan including sample size justification and interim data analysis.
- Early stopping rules.

For our first aim (to compare the vaginal and urinary microbiota before and after VET in women with rUTI), the primary outcome will be the relative abundance of Lactobacilli in the vagina and in urine. We hypothesize that after VET, the vaginal and urinary microbiota will exhibit significantly increased relative abundance of Lactobacillus and of key Lactobacillus spp. (*L. crispatus*, *L. gasseri*, *L. jensenii*, *L. iners*). Separately for each taxon and species, we will determine whether the pre-to-post change in relative abundance is significantly different from zero by paired t-test and Wilcoxon signed-rank sum test where appropriate. We will investigate the effect of VET on vaginal and urinary microbiota taxa separately. We will repeat these analyses using absolute taxa abundances estimated by pan-bacterial 16S qPCR, with a focus on key lactobacilli (e.g. *L. crispatus* and *L. iners*), and, where possible, for other bacteria of interest, including those responsible for most community-acquired UTI (*Escherichia*, *Klebsiella* and other uropathogens).

Related to the primary aim is the concentration of lactic acid in the vagina, which reflects synthesis by Lactobacilli. Therefore, we will also compare D-lactic acid concentrations in the vagina before and after VET in women with rUTI. We hypothesize that in the vagina, D-lactic acid concentration will increase. We will use similar statistical methods (as described above for aim 1) for this additional comparison.

Our second aim is to compare host immune responses, by measuring vaginal and urinary soluble mediators of inflammation (SMIs), before and after VET in women with rUTI. The specific SMIs of interest are shown in the table that follows:

Th1 associated (IFN- $\gamma$ , IL-12)	Th2 associated (IL-4, IL-6, IL-10)
Th17 associated (IL-17, IL-23)	Inflammation/macrophage activating (TNF- $\alpha$ , IL-8, IL-1 $\beta$ )

We hypothesize that after VET, vaginal and urinary samples will show decreased SMIs associated with neutrophil and macrophage activity and Th2-associated cytokines, with concomitant increases in Th1 and Th17 related pathways. Separately for each SMI, we will test whether these pre-to-post VET changes are significantly different from zero using paired t-tests or Wilcoxon signed-rank sum tests as appropriate. SMI values will be natural log-transformed. SMI values below the lower limit of detection will be imputed using the lower limit of detection of the laboratory assay divided by the square root of 2. As the SMI expression in the vagina and bladder are not well-characterized, we will also perform descriptive and exploratory analyses of the distribution of each SMI, by pre-post status, with percentile plots and generalized gamma models using graphical approaches. Use of the generalized gamma models will facilitate a more complete exploration of these highly regulated SMI markers.

All of these outcomes will then be compared to observed rates of UTI recurrence in the study population. This comparison will provide preliminary data to support a future RCT of VET in women with rUTI. For this analysis, observed UTI events will be considered as a function of “biomarkers”, including vaginal and urinary microbiota and SMIs, as well as

vaginal lactic acid. We will compare women who remain UTI free versus those who experience recurrence with respect to differences in microbiota taxa abundances (relative and absolute) and SMI concentrations. These comparisons will be performed with t-tests, Mann-Whitney test, or Chi-squared tests as appropriate.

We will recruit 50 women for this trial. With loss to follow-up, we conservatively estimate that 40-45 women will provide complete data. At 80% power and alpha of 0.05, we anticipate that we will have sufficient power to detect a 17% to 19% change in *Lactobacillus spp* relative abundance in the vaginal microbiota pre-to-post VET. Prior research suggests that we are likely to observe much larger changes in vaginal samples (>30%) with VET. Furthermore, with a sample size of 40 to 50 women, we will be able to estimate the mean change in *Lactobacillus spp* relative abundance from pre-to-post VET to within  $\pm 11.6\%$  to  $\pm 12.9\%$  with 95% confidence interval.

We are not planning interim analyses. Early stopping rules do not apply.

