### 2. Objectives (include all primary and secondary objectives)

The three aims of this proposal are:

1. **To compare the vaginal and urinary microbiota before and after VET in women with rUTI.** Hypothesis: After VET, vaginal and urinary microbiota will exhibit

*significantly increased relative abundance of key Lactobacillus spp. (L. crispatus, L. gasseri, L. jensenii, L. iners). Vaginal D-lactic acid concentration will increase and pH will decrease.*

**2. To compare host immune responses, by measuring vaginal and urinary soluble mediators of inflammation (SMIs), before and after VET in women with rUTI.**

*Hypothesis: after VET, vaginal and urinary samples will show decreased SMIs associated with neutrophil and macrophage activity and Th2-associated cytokines, with concomitant increases in Th1 and Th17 related pathways.*

**3. To acquire preliminary data regarding vaginal and urinary markers that distinguish women who remain UTI-free after VET versus those who continue to experience UTI recurrence**

**3. Background** (briefly describe pre-clinical and clinical data, current experience with procedures, drug or device, and any other relevant information to justify the research)

Each year in the U.S., urinary tract infection (UTI) is the cause of 8 million ambulatory and 1 million ED visits. Postmenopausal women are disproportionately impacted: 13% of female Medicare beneficiaries experience  $\geq 1$  UTI annually. Furthermore, among older women who experience UTI,  $>40\%$  experience chronic recurrent UTI (rUTI) (defined as UTIs that recur  $\geq 2$  times per 6 months or  $\geq 3$  per 12 months). Prevention of UTI recurrence is crucial for older women with rUTI, yet effective options are limited. **American Urologic Association guidelines recommend two options to reduce recurrence: vaginal estrogen therapy (VET) or daily low dose antibiotics. While daily antibiotic prophylaxis is effective, concerns regarding side effects and emergence of antibiotic resistance limit its use. Thus, VET prophylaxis is first line for rUTI prevention in postmenopausal women.** Several clinical trials demonstrate that 50% of women will continue to experience rUTI recurrence despite VET. At present, it is unknown why some women benefit while others do not and the mechanisms for treatment success are unknown.

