Aims 1 and 2 will identify “biomarkers” that are significantly impacted by VET. **The goal of Aim 3 is to compare these biomarkers between women who continue to experience rUTI versus those who remain UTI-free on VET.** These comparisons will provide preliminary data to support a future RCT of VET in women with rUTI. Specifically, those bio-markers which show the greatest promise to distinguish successful rUTI

prevention will then be rigorously evaluated in a future larger and adequately powered clinical trial to definitively identify the predictors of and the biological conditions associated with successful prevention of UTI recurrence among susceptible women.

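### Aim 3 is to find the most promising markers of UTI-free response, but Section 7 plans only group-difference tests, with no estimate of discrimination, no interval and no allowance for selection

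*Combined protocol and SAP*

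**What the plan says.** Section 2 (Objectives) states Aim 3 as: "To acquire preliminary data regarding vaginal and urinary markers that distinguish women who remain UTI-free after VET", set against those who continue to have recurrences. The Aim 3 paragraph that closes Section 3 (Background) gives the purpose. Aims 1 and 2 identify markers changed by vaginal estrogen, and these are compared between the two outcome groups. The paragraph then singles out "those bio-markers which show the greatest promise to distinguish successful rUTI". A later and larger trial with adequate power is to test them.

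Section 7 (Study Statistics) repeats the purpose: "This comparison will provide preliminary data to support a future RCT of VET in women with rUTI". It says that women who stay UTI-free will be compared with those who recur on taxa abundances (relative and absolute) and SMI concentrations, and it counts vaginal lactic acid among the biomarkers. The method is one sentence: "These comparisons will be performed with t-tests, Mann-Whitney test, or Chi-squared tests as appropriate".

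The power statement, "At 80% power and alpha of 0.05, we anticipate that we will have sufficient power to detect a 17% to 19% change", concerns the pre-to-post change in vaginal Lactobacillus, as does the precision statement after it. Neither covers Aim 3. No section gives a discrimination measure, an interval, a selection rule, internal validation or shrinkage for the Aim 3 comparison.

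**The concern.** The question in Aim 3 is how well a marker separates two groups and which markers do so best. A t-test or Mann-Whitney p-value answers a different question, namely whether the groups differ at all. In small groups it says little about the size of the separation or its uncertainty.

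Selection adds a second problem. When the leading marker is chosen from many noisy estimates in the same women, its raw estimate is biased upward, because the choice favours markers that chance has helped. This is bias in an estimate, not an error rate, so adjusting p-values for multiplicity would not correct it. At stake is the quality of the preliminary data: a marker may look promising when it is not, or a real one may look much stronger than it is.

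**Working it through.** **Inputs from the documents**
- Completers: "we conservatively estimate that 40-45 women will provide complete data" (Section 7).
- Recurrence: "50% of women will continue to experience rUTI recurrence despite VET" (Section 3).
- Candidates (Section 7): 10 SMIs at 2 sites = 20; Lactobacillus plus 4 species at 2 sites = 10; D-lactic acid = 1. Total 31. Counting absolute as well as relative abundance adds 10, giving 41. Uropathogens would add more. The Aim 1-2 filter in Section 3 would reduce the count by an unknown amount.

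**Assumptions, not in the documents**
- Two-sided alpha of 0.05.
- Normally distributed markers with pairwise correlation 0 to 0.5.
- The leading marker is the one with the largest observed separation.

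**1. The plan's own figures.** The SD is not stated. From the half-width, SD = half-width × √n / 1.96:
- n = 40: 12.9 × √40 / 1.96 = 41.6 points
- n = 50: 11.6 × √50 / 1.96 = 41.8 points

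Detectable change = (1.96 + 0.84) × SD / √n:
- n = 40, SD 41.8: 18.5 points
- n = 45, SD 41.6: 17.4 points

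This agrees with the stated 17% to 19%. The two statements are consistent with each other, but they say nothing about Aim 3.

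**2. Group size in Aim 3.** 40 × 0.5 = 20 and 45 × 0.5 = 22.5, so about 20 to 23 per group.

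**3. What a two-group test can show at 20 v 20.**
- Smallest observed standardised difference reaching p < 0.05: t(0.975, 38 df) × √(2/20) = 0.64.
- Difference detectable with 80% power (noncentral t): d = 0.91. With AUC = Φ(d/√2), that is an AUC of 0.74.
- Power for a true d of 0.5 (AUC 0.64): 34%.
- If that d of 0.5 does reach p < 0.05 in the right direction, the observed d averages 0.87. Reporting only significant markers would therefore overstate the effect even for a single marker.

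**4. Precision.** The 95% half-width for an AUC at 20 v 20 (Hanley-McNeil standard error) is ±0.18 at AUC 0.50, ±0.16 at 0.70 and ±0.15 at 0.75.

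**5. Selection, by simulation at 20 v 20.**

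| Candidates | True signal | Mean observed AUC of leading marker | Mean true AUC of that marker |
|---|---|---|---|
| 5 | none | about 0.64 | 0.50 |
| 10 | none | 0.66-0.67 | 0.50 |
| 31 | none | 0.69-0.71 | 0.50 |
| 10 | five at AUC 0.64 | 0.72-0.74 | 0.62-0.63 |
| 31 | five at AUC 0.64 | 0.73-0.75 | 0.59-0.60 |

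Ranges run over correlation 0 to 0.5. At 22 v 23 the row for 31 candidates without signal becomes 0.68-0.70.

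**6. How far a bootstrap correction goes.** Optimism correction that repeats the ranking in each resample (31 markers, 20 v 20) brings the leading marker to an average of 0.56-0.58 when no marker discriminates (true 0.50). With five true markers it gives 0.62-0.63 (true 0.59-0.60). Most of the optimism goes, but not all.

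**The case against.** The strongest reply is that Aim 3 is openly preliminary and that Section 3 sends the chosen markers to a larger, adequately powered trial. Independent confirmation is the main protection against a false winner. That stands, and it limits the harm. It does not make the raw estimate unbiased, and preliminary estimates are gathered to plan what follows.

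The second reply is that Section 3 restricts Aim 3 to markers changed in Aims 1-2, so 31 candidates may be too many. This also stands: the size of the bias depends on a count that cannot be known in advance. Section 7 does not repeat the filter, however, and the bias is still visible with 5 or 10 candidates.

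Three stronger readings are tempting but not supported:
- **That markers will be picked by p-value.** The documents give no selection rule. Tests are simply the only method listed.
- **That an inflated effect will be handed on.** No section says that an Aim 3 effect size will be carried forward. The harm arises only if the raw estimate is used.
- **That the future RCT will be undersized.** Its endpoint and sizing parameter are not described. A sample size computed from a marker's AUC belongs to a hypothetical marker comparison, not to that trial.

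**Conclusion.** The point holds as a gap between the goal of Aim 3 and its analysis. Section 7 would not measure how well any marker discriminates, and the raw estimate for a selected marker would be optimistic. With no true signal, the leading AUC averages about 0.64 to 0.71 for 5 to 31 candidates, against a true 0.50. With five real markers among 31, the leader shows 0.73-0.75 against a true value of about 0.60.

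These sizes rest on the inferred 20 v 20 split, normal markers, correlation 0-0.5 and the assumed candidate counts. The split could differ: Section 4a places Aim 3 in the second 12 weeks but tracks episodes over 24. The direction of the bias does not depend on these choices. No Aim 1 or Aim 2 conclusion is affected. This is a worthwhile, low-cost improvement, not a flaw that undermines the trial.

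**What to change.** In the Aim 3 paragraph of Section 7:
1. For every candidate marker compared, not only the significant ones, report the AUC (Mann-Whitney U divided by n1 × n2) or the standardised difference, with a 95% CI.
2. For the leading markers, add a bootstrap optimism-corrected value, with the whole selection step, including any Aim 1-2 filter, repeated in each resample.
3. State that the corrected value may still be somewhat optimistic and that uncorrected estimates should not be used as planning values. Sizing the later trial can be left to its own protocol.

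The cost is a few lines of plan text and slightly more analysis; no extra women, specimens or visits are needed. The reported discrimination will look less favourable, and the intervals will be wide.

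### Precision is quoted for 40 to 50 women although 40-45 are expected to give complete data, so the ±11.6% end assumes no losses

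*Combined protocol and SAP*

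**What the plan says.** The sample-size paragraph of section 7 (Study Statistics) makes four statements in sequence.

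- Recruitment: "We will recruit 50 women for this trial".
- Retention: "With loss to follow-up, we conservatively estimate that 40-45 women will provide complete data".
- Power: "At 80% power and alpha of 0.05, we anticipate that we will have sufficient power to detect a 17% to 19% change in" vaginal Lactobacillus relative abundance. No n is attached to either end of that range.
- Precision: "with a sample size of 40 to 50 women, we will be able to estimate the mean change in" Lactobacillus relative abundance to within ±11.6% to ±12.9%, "with 95% confidence interval".

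Earlier in the same section, the change is to be tested "by paired t-test and Wilcoxon signed-rank sum test where appropriate". Sections 4a and 4c place specimen collection at enrolment and at 12 weeks only. The SD of the change is not given, nor whether the percentages are percentage points or relative changes.

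**The concern.** The retention and precision statements use different numbers of women. The mean change is a paired quantity, and a woman without a 12-week specimen contributes nothing to it. The plan describes no imputation of missing pairs that could bring the count back to 50. The upper count in the precision statement is therefore the number recruited, while the plan itself expects to analyse 40-45.

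The power and precision statements are the whole quantitative justification of the sample size. If the better end of a range is computed at full retention, a reader will expect more precision than the plan's own retention estimate supports. Without an SD, the reader can see this only by back-solving.

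**Working it through.** **Inputs.** All come from section 7: 50 recruited; 40-45 with complete data; half-widths ±11.6% and ±12.9% for 40 to 50 women; detectable change 17% to 19% at 80% power and alpha 0.05; paired t-test. Assumptions: percentages are percentage points, alpha is two-sided, and the SD of change is back-solved because the plan states none.

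**Step 1: reproduce the stated precision.** Half-width = 1.96 × SD / √n, so SD = half-width × √n / 1.96. Each stated half-width is allowed its rounding interval (12.85-12.95 and 11.55-11.65).

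| Reading | Implied SD |
|---|---|
| ±12.9 at n=40 | 41.46 to 41.79 |
| ±11.6 at n=50 | 41.67 to 42.03 |
| ±11.6 at n=45 | 39.53 to 39.87 |

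The first two intervals overlap at 41.67 to 41.79, so one SD of about 41.7 gives both stated figures at n=40 and n=50. The third does not overlap the first, so ±11.6 cannot be the n=45 figure.

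A check that needs no SD: the ratio of the half-widths is 12.9 / 11.6 = 1.112. This is close to √(50/40) = 1.118 and far from √(45/40) = 1.061. Taking rounding to its limit, the upper count must be at least 40 × (12.85/11.65)² = 48.7. Of the counts the plan names, only 50 fits.

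With t quantiles in place of 1.96, n=40 implies an SD of 40.18-40.49 and n=50 implies 40.64-40.99. These do not overlap, so the plan's evident method is the normal multiplier.

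**Step 2: precision at the expected number of pairs.** With SD 41.7:

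- n=40: 1.96 × 41.7 / √40 = 12.92
- n=45: 1.96 × 41.7 / √45 = 12.18
- n=50: 1.96 × 41.7 / √50 = 11.56

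At 40-45 pairs the range is ±12.2 to ±12.9. The favourable end moves by 12.2 − 11.6 = 0.6 points, and the unfavourable end does not move.

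**Step 3: detectable change, if the same SD applies.** Two-sided paired t-test (noncentral t), alpha 0.05, power 80%. The normal approximation is (1.96 + 0.842) × SD / √n.

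| SD and method | n=40 | n=45 | n=50 |
|---|---|---|---|
| 41.7, paired t-test | 18.9 | 17.8 | 16.9 |
| 41.7, normal approximation | 18.5 | 17.4 | 16.5 |
| 40.82, paired t-test | 18.54 | 17.43 | 16.50 |
| 41.78, normal approximation | 18.51 | 17.45 | 16.55 |

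In the first row, 17% to 19% is the n=50 to n=40 range, and power for a 17-point change is 71% at n=40, 76% at n=45 and 81% at n=50. In the last two rows, 19% falls at n=40 and 17% at n=45.

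**Step 4: consequence for the anticipated effect.** The plan expects changes above 30%. At SD 41.7, paired t-test power for a 30-point change is 99.3% at n=40 and 99.7% at n=45.

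**The case against.** The precision statement names its own n, and its figures are correct for that n. It runs openly from the worst expected retention to full retention, with the unfavourable end already at n=40. This stands: the fault is a mismatch with the retention estimate, not a miscalculation.

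The plan does not define complete data. Follow-up for UTI runs to 24 weeks, but the specimen pair is finished at week 12, and section 4g encourages women who stop treatment to stay in the trial. If the term includes 24-week follow-up, vaginal pairs could exceed 45. This is possible, but the plan does not say so, and 40-45 is the only retention figure it gives.

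A reader might infer that 17% is likewise a no-loss figure. The documents do not establish this. The power statement directly follows the 40-45 estimate and gives no SD or n. An SD of 40.82, less than one point below 41.7, puts 17% at n=45 with the exact t-test, although that SD does not reproduce the precision figures by the 1.96 method (12.65 at n=40). A normal approximation with SD 41.78, at the edge of the rounding interval but inside it, does the same.

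A reader might also want t quantiles, which at SD 41.7 give ±12.5 (n=45) to ±13.3 (n=40). That changes the plan's method and would make its sound n=40 figure look wrong. It is a separate preference and not needed here.

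**Conclusion.** The point holds for precision. The plan expects 40-45 women with complete data, and ±11.6% matches 50 pairs, that is, no losses. On the plan's evident method, precision at the expected count is about ±12.2 to ±12.9 percentage points. This rests on reading complete data as complete specimen pairs and on a back-solved SD of about 41.7. The mismatch in counts itself is on the page and needs no SD.

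For the detectable change the point is conditional. If the same SD applies, the planned paired t-test detects about 18 to 19 points at 40-45 pairs (17.8 at n=45, 18.9 at n=40). The plan gives too little to say which n lies behind 17%.

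The consequence is minor. A reader might take this as a sign that the trial is too small, and the figures do not support that: power for a 30-point change stays above 99% at n=40.

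**What to change.** In the sample-size paragraph of section 7:

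1. Quote precision at the expected 40-45 complete pairs, about ±12.2 to ±12.9 percentage points by the present method. Alternatively, keep ±11.6 and label it as the case with no losses.
2. State the assumed SD of the pre-to-post change and its source. Only the sponsor can supply this. The 41.7 used here is back-solved for checking and should not be entered as the sponsor's assumption.
3. Recheck the 17% end of the detectable change at 40-45 pairs with that SD, and name the n behind each end.
4. Say whether the percentages are percentage points.

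The cost is a sentence or two of text and slightly less favourable figures. Enrolment and procedures stay as they are.

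### The stated 95% precision of ±11.6% to ±12.9% for 40 to 50 women does not fit t intervals with one SD; the n=40 figure is slightly too narrow

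*Combined protocol and SAP*

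**What the plan says.** All the relevant text is in Section 7, Study Statistics, of the combined protocol and SAP.

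- **Analysis.** For Aim 1, each taxon is tested for whether the "pre-to-post change in relative abundance is significantly different from zero by paired t-test and Wilcoxon signed-rank sum test where appropriate".
- **Numbers.** Fifty women are recruited, and "we conservatively estimate that 40-45 women will provide complete data".
- **Power.** "At 80% power and alpha of 0.05, we anticipate that we will have sufficient power to detect a 17% to 19% change in" vaginal Lactobacillus relative abundance. This sentence does not say which sample sizes the two figures belong to.
- **Precision.** "with a sample size of 40 to 50 women, we will be able to estimate the mean change in" Lactobacillus relative abundance to within ±11.6% to ±12.9% "with 95% confidence interval". The narrower figure must belong to 50 women and the wider to 40.

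The section gives no SD for the paired change, no multiplier and no formula for the interval.

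**The concern.** The trial will estimate the SD of the change from its own 40 to 50 differences. The interval for a mean that matches a paired t-test uses the t multiplier on n−1 degrees of freedom: 2.023 at n=40 and 2.010 at n=50. The printed half-widths behave as if one fixed multiplier had been used at both sample sizes. If that multiplier is below the t value, the interval reported at the end will be wider than promised for the same SD.

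This is the plan's only statement of precision, and it concerns the primary outcome. Without the SD, a reader cannot check it directly.

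**Working it through.** **Inputs.** From Section 7: half-widths 12.9 (n=40) and 11.6 (n=50), 95% confidence, 80% power, alpha 0.05, and detectable changes of 17% to 19%. Assumed: two-sided alpha and interval, printed figures rounded to the last digit shown, one SD throughout, and 19% belonging to n=40, the smallest number in the paragraph. The SD is not stated, so it is solved for.

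**Step 1: which SD gives each printed half-width?** Half-width = multiplier × SD / √n, so SD = half-width × √n / multiplier. Rounding allows 12.85 to 12.95 at n=40 and 11.55 to 11.65 at n=50.

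| Multiplier | SD from n=40 | SD from n=50 | Common SD |
|---|---|---|---|
| 1.96 | 41.47 to 41.79 | 41.67 to 42.03 | 41.67 to 41.79 |
| 2.0 | 40.64 to 40.95 | 40.84 to 41.19 | 40.84 to 40.95 |
| t(n−1): 2.0227, 2.0096 | 40.18 to 40.49 | 40.64 to 40.99 | none |

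So the plan's pair is reproduced with 1.96 at SD 41.7 (1.96 × 41.7 / √40 = 12.92; 1.96 × 41.7 / √50 = 11.56) and with 2.0 at SD 40.9 (12.93 and 11.57).

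**Step 2: the same check without any SD.** The printed ratio 12.9/11.6 is 1.112. Rounding allows 12.85/11.65 = 1.103 to 12.95/11.55 = 1.121. A fixed multiplier requires √(50/40) = 1.118, which is inside. The t multipliers require (2.0227/2.0096) × 1.118 = 1.125, which is outside.

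**Step 3: use the power figure to bound the SD at n=40.** For a paired t-test with 80% power at n=40, the detectable change is 0.4543 × SD (noncentral t). To print as 19 it must be at least 18.5, so SD ≥ 18.5 / 0.4543 = 40.7. By the normal approximation the factor is (1.960 + 0.842)/√40 = 0.4430, so SD ≥ 41.8. The t half-width at n=40 is then at least 2.0227 × 40.73 / √40 = 13.02.

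The SDs that would make ±12.9 a correct t half-width at n=40 (40.18 to 40.49) give a detectable change of 18.3 to 18.4, which prints as 18, not 19.

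At the largest SD that fits the printed pair (41.79), the t half-width at n=40 is 2.0227 × 41.79 / √40 = 13.37. The range is therefore about ±13.0 to ±13.4. The power figure taken alone would allow an SD up to 42.9 and a half-width up to ±13.7, but no multiplier in the table gives the printed pair at such an SD.

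**Step 4: t half-widths under the two readings.**

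| SD | n=40 (printed 12.9) | n=45 | n=50 (printed 11.6) |
|---|---|---|---|
| 41.7 (1.96 reading) | 13.34 | 12.53 | 11.85 |
| 40.9 (2.0 reading) | 13.08 | 12.29 | 11.62 |

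Under the 1.96 reading the t intervals are 3.2% wider at n=40 and 2.5% wider at n=50 (2.0227/1.96 and 2.0096/1.96). An interval built with 1.96 would cover 94.3% and 94.4%. A t half-width of no more than ±12.9 would take 43 complete pairs (2.0181 × 41.7 / √43 = 12.83; at 42 pairs it is 13.00). Under the 2.0 reading the n=50 figure is right as printed.

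**The case against.** The strongest reply is that this treats an inference as a fact, and over a trivial amount.

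- **The multiplier is not printed.** A reader might infer that 1.96 was used and that every stated half-width is therefore too narrow. The documents do not support this: 2.0 with an SD near 40.9 fits both figures equally well, and the n=50 figure is then correct. This part of the reply stands.
- **Mixed methods are not shown.** A reader might also infer that the power figure uses t and the precision figure uses the normal distribution, because at SD 41.7 noncentral t gives 18.9 and 16.9 while the normal approximation gives 18.47 and 16.5. But at SD 41.77, still within the admissible range, the normal approximation gives 18.50 and 16.55, which also print as 19 and 17. Whole-percent figures cannot separate the two, so this stands as well.
- **No t interval is promised.** Section 7 names the paired t-test, with Wilcoxon where appropriate, for testing and is silent on the interval. That is so, but the t interval is the one that corresponds to the named parametric test when the SD is estimated.
- **The exclusion of t is a matter of rounding.** One SD does fit t intervals at n=40 and 49, or at 41 and 50, and SD 40.6 comes within 0.1 point of both printed figures (12.98 and 11.54). But 40 and 50 are the numbers stated, and SD 40.6 gives a detectable change at n=40 of 18.4, which would not print as 19.
- **Planning figures are approximate.** An error of about 3% in the guessed SD would matter as much. True, and it keeps the point small, but it does not make the printed figure right.

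**Conclusion.** The point holds as a small error in one sentence. The printed pair is not a pair of t half-widths from a single SD at n=40 and n=50. The n=40 figure is too narrow on any SD that agrees with the printed 19% detectable change: about ±13.0 to ±13.4 rather than ±12.9. This rests on 19% belonging to n=40, two-sided 5% calculations and ordinary rounding. It does not depend on whether the 17% belongs to n=45 or n=50, because the bound uses only the 19%. The n=50 figure is too narrow, at about ±11.9, only under the 1.96 reading.

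The size is about 0.1 to 0.4 percentage points. The 50-woman target, the power statement and the comparison with an expected change above 30% are unaffected. The n=40 end matters most, since it is the plan's own lower estimate of women with complete data.

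**What to change.** In the sample-size paragraph of Section 7, state the assumed SD of the paired change and its source, and say that the interval is a t interval. Recompute the half-widths from that SD with t(n−1) multipliers at the numbers of complete pairs quoted. If the SD is 41.7, for example, the figures are ±13.3 at n=40, ±12.5 at n=45 and ±11.9 at n=50. These figures are illustrative: 41.7 is inferred here, and the sponsor should use the SD actually assumed.

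The cost is an edit to one sentence and a slightly less favourable stated precision. Nothing in the conduct of the trial changes.
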